8.2. Secondary Efficacy Analysis

[figure not shown]
The following secondary endpoints will be analyzed in the mITT, ITT, cITT, and ITT-mild analysis sets: iADRS, MMSE, NPI-10, and ZBI. The MMRM model as described for the primary analyses will be used, with the exception for MMSE where the baseline value for the endpoint being analyzed is the MMSE baseline; therefore, the model for MMSE will include the categorical fixed effects of treatment group, Visit, and pooled site, along with the continuous, fixed covariate of baseline MMSE score and the interactions of treatment group and baseline MMSE with Visit.

The CDR-SB is collected only at Screening and Week 76 or ET/ED. Therefore, the CDR-SB will be analyzed using ANCOVA with a model that includes treatment group, pooled site, and baseline MMSE.

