# 11.3.3 Other Secondary Analyses

The iADRS is a linear combination of scores from two well-established, widely accepted, therapeutically sensitive measures of AD: the ADAS-Cog and ADCS-iADL (the instrumental component of the ADCS-ADL). The iADRS has been validated and statistical properties of the composite performance have been described. All items of the ADAS-Cog12 and the ADCS-iADL will be included to generate this primary efficacy composite measurement without additional weighting.

Secondary clinical endpoint data (iADRS, NPI, MMSE, and ZBI) measured repeatedly will be analyzed by linear mixed models for repeated measurements, as described above for the primary analysis.

Plasma assays may include P-tau181 and/or P-tau217, SavaDx, neurofilament light chain, and other biomarkers. All plasma biomarker data and MRI data measured repeatedly will be analyzed by linear mixed models for repeated measurements, as described above for the primary analysis.

CSF biomarker endpoints to be analyzed currently include: 1) neurogranin, 2) neurofilament light chain, 3) total tau, 4) P-tau181 and/or P-tau217, 5) sTREM2, and 6) A $\beta_{42}$ . Additional CSF biomarkers may be measured. All CSF biomarker data, PET imaging data, and CDR-SB will be analyzed using ANCOVA models with treatment group as a factor and the baseline value of the corresponding endpoint as a covariate.

All secondary analyses will be conducted using two-sided tests at the alpha = 0.05 level of significance, with no adjustments for multiplicity.

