2.2. Sample Size and Power

The sample size for this study was originally determined as follows.

Planned enrollment was approximately 1083 participants with mild-to-moderate AD. The sample size was determined by a power analysis of ADAS-Cog using data from a similar population over 76 weeks. This analysis determined that the comparison between an active arm and placebo requires group sizes of 289 to provide 90% power to detect a 45% difference from placebo at 76 weeks, based on the use of a two-sided test at the alpha = 0.05 significance level. The power calculation assumes a true mean change from baseline for placebo of 6.0 points and a standard deviation of 10.0 points. Assuming a drop-out of 20%, each treatment group should enroll approximately 361 participants.

Learnings from analyses of the sister study, and results from other development programs in AD led to change in the primary analysis population for this study to include in the primary analysis only those participants with >= 44 pg/ml P-tau181 at baseline, or other confirmation of amyloid pathology (e.g., amyloid PET). Based on results of study PTI-125-07, it is anticipated that the reduction in sample size will be offset by an increase in treatment effect such that the study will have at least as much power as originally planned.

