3.2. Estimands

The primary estimand for the primary efficacy endpoints is defined as follows:

Population	The original population was specified as: Participants with mild-to-moderate AD dementia who meet the study's inclusion and exclusion criteria. The
	population of interest was changed after early termination, but while still

Version 1.0 | 28-Feb-2025 Page 15 of 56

	blinded, to: Participants with mild-to-moderate AD dementia who meet the study's inclusion and exclusion criteria, and who have baseline P-tau181 ≥ 44 pg/ml or other evidence of amyloid pathology.
Treatments	Simufilam 100 mg twice daily or placebo (50mg twice daily is secondary).
Endpoints	ADAS-Cog12 (range $0-80$, higher score indicates greater impairment) and ADCS-ADL (range $0-78$, lower score indicates greater impairment).
Summary Measure	Difference between treatments in least squares (LS) mean change from baseline to Week 76.
Intercurrent Events	All deviations from the intended dosing regimens and use of concomitant medication will be handled using a treatment policy strategy. Early study discontinuation will be consistently accounted for using a hypothetical strategy to estimate what would have been observed if the participant had not discontinued.

The estimands for the multiplicity controlled secondary efficacy endpoint(s) are similar to the co-primary estimands. Each secondary estimand has the following components:

Population	The original population was specified as: Participants with mild-to-moderate AD dementia who meet the study's inclusion and exclusion criteria. The population of interest was changed after the early termination, but while still blinded, to: Participants with mild-to-moderate AD dementia who meet the study's inclusion and exclusion criteria, and who have baseline P-tau181 ≥ 44 pg/ml or other evidence of amyloid pathology.
Treatments	Simufilam 100 mg twice daily or placebo (50 mg twice daily is secondary)
Endpoints	iADRS, NPI-10, MMSE, CDR-SB, ZBI
Summary Measure	Difference between treatments in LS mean change from baseline to week 76
Intercurrent Events	All deviations from the intended dosing regimens and use of concomitant events medications will be handled using a treatment policy strategy. Early study discontinuation will be consistently accounted for using a hypothetical strategy to estimate what would have been observed if the participant had not discontinued.

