All statistical comparisons will be based on LS means from the relevant contrasts in the mixed model for repeated measurements (MMRM) or analysis of covariance (ANCOVA).

The data from nominal/scheduled protocol clinic visits will be included in visit-based summary tables. Unscheduled assessments, if they occur, and the ET visit data will be mapped to scheduled assessments according to the visit windows defined in section 6.1.5 for all safety and efficacy analyses. See Section 6.1.4 and 6.1.5 of this SAP for more details.

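### The CDR-SB ANCOVA omits the baseline CDR-SB covariate that the protocol specifies, and the SAP does not settle whether early-termination values count as Week 76

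*SAP*

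**What the plan says.** **Model.** SAP 8.2 notes that "The CDR-SB is collected only at Screening and Week 76 or ET/ED" and therefore uses ANCOVA with treatment group, pooled site and baseline MMSE. SAP 8.3 uses the same three terms for CSF and imaging markers that have a single post-baseline value. Protocol 11.3.3 describes the ANCOVA for CSF, PET and CDR-SB as having treatment as a factor and the "baseline value of the corresponding endpoint as a covariate". SAP section 10, on changes from the planned analysis, is marked not applicable.

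**Estimand.** SAP 3.2 defines the secondary estimands, CDR-SB included, as the treatment difference in change to Week 76. It adds: "Early study discontinuation will be consistently accounted for using a hypothetical strategy to estimate what would have been observed".

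**Timing of early-termination (ET) values.** Protocol section 9 asks for a CDR at early discontinuation unless one was done in the last 30 days. SAP 4.2 says "the ET visit data will be mapped to scheduled assessments according to the visit windows" of section 6.1.5, and the same sentence covers both safety and efficacy analyses. Section 6.1.5 discards an ET assessment that falls in a window where that assessment is not scheduled. That clause and the day-range tables come under the safety summaries. The efficacy paragraphs that follow say only that visits go to the nearest scheduled visit and that values sharing a window are averaged.

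**Role.** SAP 6.1.3 tests CDR-SB second of five secondary endpoints in the 100 mg arm, after iADRS and before ZBI, MMSE and NPI-10.

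**The concern.** There are two separate problems.

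First, the covariate. CDR-SB is the only one of the five ordered secondary endpoints whose SAP model does not adjust for its own baseline: the MMRM does so for iADRS, ZBI and NPI-10, and baseline MMSE does so for MMSE. Randomisation is stratified on MMSE only, so nothing in the design balances baseline CDR-SB. With complete data the omission does not bias a randomised comparison. It does lose precision, leaves chance imbalance unadjusted, and departs from the protocol without saying so.

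Second, the timing. SAP 6.1.4 acknowledges that the early stop creates more missing data than expected, so ET values could be numerous. Two programmers following the SAP could build different CDR-SB data sets, one with ET values entered as Week 76 and one without them. The model has no term for follow-up time, and no missing-data method or imputation-based sensitivity analysis is given for this endpoint. The copy-reference imputation in 8.1.1 is for the co-primary endpoints.

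At stake is the interpretation of a formally tested endpoint. If it misses significance, ZBI, MMSE and NPI-10 in the 100 mg arm are declared non-significant. The 50 mg and mild-subgroup tests of those endpoints depend on the 100 mg result.

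**Working it through.** **1. How the timing rules act on one value.** Take an ET visit at Week 20, which is Day 20 × 7 + 1 = 141.
- Table 2.1 places Day 141 in the Week 16 window (Day 72-155). CDR is not scheduled at Week 16, so the discard clause, if it applies to efficacy, removes the value.
- If windows follow the assessment's own schedule, as Table 2.2 does for ECG, the only post-baseline CDR visit is Week 76, and the value becomes a Week 76 value.
- The planned pooled Week 52 CDR-SB table (T14.2.7.6.1) points away from the discard clause. This study schedules no Week 52 CDR, so only ET values could supply its data.

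An ET visit at Week 72 (Day 72 × 7 + 1 = 505) falls in Day 492-575 and counts as Week 76 either way. The dispute concerns values before Day 492, about Week 70 (491/7 = 70.1).

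**2. The plan's own power figure.** This is for ADAS-Cog; none is given for CDR-SB. Inputs from SAP 2.2: a placebo change of 6.0 points with an SD of 10.0, a two-sided 5% test, and "group sizes of 289 to provide 90% power to detect a 45% difference from placebo at 76 weeks". The difference is 0.45 × 6.0 = 2.7 points, a standardised effect of 2.7/10 = 0.27.

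n = 2 × (1.960 + 1.2816)² / 0.27² = 288.3, so 289 per arm. This reproduces. SAP 2.2 continues: "Assuming a drop-out of 20%, each treatment group should enroll approximately 361 participants". 289/0.8 = 361.25, which agrees with 361 apart from rounding.

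**3. Illustration of the two readings.** Assumptions not in the documents: CDR-SB has the same 0.27 effect, the arms diverge linearly, the SD is constant over follow-up, and a share f of values comes from ET visits at mean week t.

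- Early values used: retained fraction k = 1 − f(1 − t/76), with all 361 per arm contributing. Power = Φ(k × 0.27 × √(361/2) − 1.96).
- Early values dropped: k = 1 and n = 361(1 − f). Power = Φ(0.27 × √(n/2) − 1.96).

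| f | k, t = 40 | Power, used, t = 40 | k, t = 20 | Power, used, t = 20 | n per arm, dropped | Power, dropped |
|---|---|---|---|---|---|---|
| 20% | 0.905 | 91% | 0.853 | 87% | 289 | 90% |
| 40% | 0.811 | 84% | 0.705 | 72% | 217 | 80% |
| 60% | 0.716 | 74% | 0.558 | 53% | 144 | 63% |

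**4. Bias with no drug effect.** Suppose 20% of placebo and 30% of active values are ET values at a mean of Week 40. The retained fractions of decline are 1 − 0.2 × 36/76 = 0.905 and 1 − 0.3 × 36/76 = 0.858. The apparent slowing is (0.905 − 0.858)/0.905 = 5.2%. At a mean of Week 20 it is 8.6%. Reversing the imbalance gives an apparent worsening.

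**5. What dropping requires.** With no intermediate CDR visits, an ANCOVA on observed Week 76 values needs missingness to depend only on treatment, site and baseline MMSE. The MMRM's missing-at-random assumption also allows dependence on observed post-baseline scores.

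**The case against.** The best defence is that the SAP does contain a time restriction. Section 4.2 extends the 6.1.5 windows to efficacy, 6.1.5 discards ET assessments in windows where they are not scheduled, and together they confine CDR-SB to the Week 76 window. A Week 20 visit is also nearest to Week 16 in the overall schedule, and where the SAP wants wider windows for one assessment it supplies a table, as for ECG. A reader who looked only at 8.2 might infer that ET values enter with no time limit at all; the documents do not support that. What stands is an ambiguity: the discard clause is in the safety text, and the efficacy text then gives different rules.

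A reader might also infer that neither reading matches the estimand. That is too strong. SAP 6.1.4 treats missingness from the stop as missing completely at random. If so, a Week 76-window ANCOVA is not biased by the stop. The mismatch left is ordinary dropout, planned at 20%.

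Nor can it be said that using ET values must cost power. At a mean of Week 40 it gives 91/84/74%, against 90/80/63% when they are dropped, because more participants contribute. It does worse at a mean of Week 20.

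Three further points limit the reach. The planned cITT table for CDR-SB (T14.2.7.3.1) sets values from 25 November 2024 onward to missing, which removes ET values caused by the stop, though it is outside the formal testing order. The consequence for later endpoints arises only if both co-primaries and iADRS are significant. For PET the timing question is narrower, because protocol 7.1.7 seeks a second scan only from those terminating after 52 weeks, and the CSF and PET endpoints are tertiary in the SAP.

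None of this answers the missing baseline covariate.

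**Conclusion.** The point holds in two parts. The omission of the endpoint's baseline value from the CDR-SB, CSF and PET ANCOVAs contradicts protocol 11.3.3 and is not recorded in SAP section 10. This needs no assumption. Its cost in precision depends on how strongly baseline CDR-SB predicts change once MMSE is in the model, which the documents do not give.

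The handling of early CDR-SB values is ambiguous rather than unrestricted. Used as Week 76, they give an estimate that is not the Week 76 difference and that unequal ET timing between arms can bias. Dropped, they cost precision, plus a stronger assumption about ordinary dropout than the MMRM makes.

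The retained-effect, power and bias figures are illustrations only. They rest on a borrowed ADAS-Cog effect and assumed ET shares and timing, and should not be cited as the size of the problem in this trial.

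**What to change.** 1. Add the baseline value of the endpoint to the ANCOVA in 8.2 (baseline CDR-SB) and in 8.3 (CSF and PET). If any departure from protocol 11.3.3 is kept, list it in section 10.
2. State that, for efficacy, only CDR assessments in the Week 76 window of Table 2.1 (Day 492-575) count as Week 76, and that others are not used as Week 76 values. Say what, if anything, this study then contributes to the pooled Week 52 CDR-SB table.
3. Name a missing-at-random method for the Week 76 values that are then missing. One suitable choice is multiple imputation using treatment, baseline CDR-SB, baseline MMSE and the ADAS-Cog12 and ADCS-ADL visit data.

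The cost is SAP wording, one added covariate and one imputation step. All the data are already collected: CDR is done at screening, and both co-primary scales at every post-baseline visit.

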6.1.2. Adjustments for Covariates

Primary efficacy analyses will include as covariates the baseline value of the endpoint being analyzed and the MMSE baseline score, along with the interaction of these covariates with Visit. Investigative site (pooled, see section 6.1.6) will also be included as a categorical fixed effect. Covariates observed to be important in post-hoc analyses of the PTI-125-07 study will also be included in sensitivity analyses. See section 8.4 for further details.

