6.1.3. Multiple Comparisons

The co-primary endpoints of ADAS-Cog12, and ADCS-ADL in the 100mg treatment arm will each be tested at p=0.05 using the mITT analysis set. Multiplicity among secondary endpoints for the 100 mg arm in the mITT analysis set will be controlled using a hierarchical, gatekeeping strategy. Secondary endpoints in the 100mg arm will be tested in the following order: iADRS, CDR-SB, ZBI, MMSE, and NPI-10. Testing will proceed in this order until the first non-significant p value (p > 0.05). The first endpoint with p > 0.05 and all subsequent endpoints in the order will be declared non-significant, and all endpoints preceding the first non-significant test will be declared significant. Endpoints that were significant in the 100mg arm will also be tested in the 50mg arm at P = 0.05.

For the set of significant endpoints in the 100 mg arm of the mITT analysis set, the corresponding endpoints in the mild subgroup (ITT-mild analysis set) will be tested. Testing for the mild cohort will proceed in the same order as for the secondary endpoints referenced above until the first non-significant p value. The first endpoint with p > 0.05 and all subsequent endpoints in the order will be declared non-significant, and all endpoints preceding the first non-significant test will be declared significant.

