8.3. Tertiary/Exploratory Efficacy Analysis

Plasma and imaging biomarkers that are collected repeatedly post-baseline will be analyzed with

Version 1.0 | 28-Feb-2025 Page 28 of 56

the MMRM analysis as described above.

CSF and imaging biomarkers that are collected only at screening/baseline and Week 76 ET/ED will be analyzed using ANCOVA with a model that includes treatment group, pooled site, and baseline MMSE.

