pre-treatment to post-treatment will be summarized in a shift table. An additional shift table of maximum ideation from pre-treatment to post-treatment will also be provided.

All C-SSRS data will be listed.

All other safety evaluations including urine drug screen results, screening laboratory assessments, Genotyping results collected at Baseline (Study Day 1), and Follow-up Phone Call data will be listed.

10. Changes from Planned Analysis

Not Applicable.

11. Other Planned Analysis

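### SAP 8.2 and 8.3 replace the endpoint's own baseline with baseline MMSE in the CDR-SB, CSF and PET ANCOVAs, against protocol 11.3.3 and undeclared, and CDR-SB is second in the gated secondary order

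*SAP*

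**What the plan says.** Protocol 11.3.3 covers CSF biomarkers, PET imaging and CDR-SB together and specifies ANCOVA "with treatment group as a factor and the baseline value of the corresponding endpoint as a covariate". It includes neither site nor MMSE.

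SAP 8.2 says "the CDR-SB will be analyzed using ANCOVA with a model that includes treatment group, pooled site, and baseline MMSE". SAP 8.3 says "CSF and imaging biomarkers that are collected only at screening/baseline and Week 76 ET/ED will be analyzed using ANCOVA with a model" containing the same three terms. By the schedule of activities, imaging measured only at baseline and Week 76 means amyloid and tau PET. Volumetric MRI is repeated and goes to the MMRM.

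Elsewhere the SAP keeps the own baseline:

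- SAP 6.1.2: "Primary efficacy analyses will include as covariates the baseline value of the endpoint being analyzed and the MMSE baseline score". This rule is written for primary analyses only.
- SAP 8.2, for iADRS, NPI-10, ZBI and MMSE: "The MMRM model as described for the primary analyses will be used, with the exception for MMSE". The MMSE exception still leaves MMSE adjusted for its own baseline.

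The secondary estimands in SAP 3.2 use this summary measure: "Difference between treatments in LS mean change from baseline to week 76". SAP 6.1.3 sets the gate: "Secondary endpoints in the 100mg arm will be tested in the following order: iADRS, CDR-SB, ZBI, MMSE, and NPI-10", stopping at the first p above 0.05. SAP section 10, on changes from the planned analysis, reads "Not Applicable".

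**The concern.** The two documents prescribe different models for the same test, with no rationale for the switch. If both co-primaries and iADRS succeed, CDR-SB is the next gate. A non-significant CDR-SB ends testing of ZBI, MMSE and NPI-10 at 100 mg, and those endpoints then cannot be carried to the 50 mg arm or to ITT-mild. The CDR-SB p-value may depend on which document is followed.

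Baseline MMSE is only a partial substitute for baseline CDR-SB. Analysing change subtracts the baseline, but any remaining slope of change on baseline stays in the error term, and chance imbalance is only partly corrected. CSF and PET are exploratory, but with 30 to 50 subjects per arm chance imbalance is largest there.

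A lesser, related point concerns SAP 8.4. It removes both the own baseline and MMSE from the two MMSE-split subgroup models, citing possible confounding with subgroup. By extension it apparently does the same for age, sex, ethnicity, race, ApoE4 and medication use. The overlap is real for continuous MMSE in an MMSE split, but it affects the subgroup main effect, not the randomised contrasts. It has no evident application to a factor such as sex. The ITT-mild analysis keeps the full primary model, and the amnestic, NPI-10 and severity-by-P-tau181 analyses state no such removal.

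**Working it through.** **The plan's own figure.** The only power calculation (protocol 11.5, SAP 2.2) is for ADAS-Cog: a difference of 0.45 × 6.0 = 2.7 points, SD 10, two-sided alpha 0.05, 90% power. n = 2 × (1.960 + 1.282)² × 10² / 2.7² = 288.3, so 289 per group, as stated. There is no such calculation for CDR-SB, CSF or PET. The 90% used below is therefore only a reference point.

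**Set-up (all correlations are assumptions).** Baseline B has SD 1 and follow-up Y has SD k. Let corr(B,Y) = ρ, |corr(MMSE,B)| = a and |corr(MMSE,Y)| = b. Site is ignored. Residual variances of the treatment contrast, up to a common factor:

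- SAP model (change given MMSE): k² + 1 − 2ρk − (bk − a)²
- Own baseline plus MMSE: k²[1 − (ρ² + b² − 2ρab)/(1 − a²)]
- Protocol model (own baseline only): k²(1 − ρ²)

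Power, starting from 90%: Φ((1.960 + 1.282)/√ratio − 1.960).

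**CDR-SB, worked cells with a = b = 0.5**

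| k | ρ | SAP | Own + MMSE | Protocol | SAP ÷ (own + MMSE) | SAP ÷ protocol |
|---|---|---|---|---|---|---|
| 1.0 | 0.7 | 0.600 | 0.480 | 0.510 | 1.25 | 1.18 |
| 1.2 | 0.7 | 0.750 | 0.691 | 0.734 | 1.085 | 1.02 |
| 1.2 | 0.8 | 0.510 | 0.499 | 0.518 | 1.022 | 0.98 |
| 1.4 | 0.8 | 0.680 | 0.679 | 0.706 | 1.001 | 0.96 |

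**CDR-SB, full grid.** k is 1.0 to 1.4 in steps of 0.1, ρ is 0.6, 0.7 or 0.8, and a and b are each 0.4, 0.5 or 0.6, giving 135 cells.

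- Against own baseline plus MMSE (the proposed remedy): minimum 1.00, median 1.0875, maximum 1.565. Power is 90% at the minimum, 87.5% at the median and 73.6% at the maximum. A ratio of 1.25 gives 82.6%.
- Against the protocol model: 0.75 to 1.25, median 1.015. Power is 89.6% at the median and 82.6% at worst. The SAP model is the more precise of the two in 53 of 135 cells.

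**CSF and PET, k = 1, a = b = 0.1.** The ratio to own baseline plus MMSE is 1.18, 1.11 and 1.05 for ρ = 0.7, 0.8 and 0.9. With 30 per arm, one standard error of baseline imbalance is √(2/30) × √(1 − 0.01) = 0.257 SD. The slope of change on baseline given MMSE is (ρ − ab)/(1 − a²) − 1, which is −0.303 at ρ = 0.7 and −0.101 at ρ = 0.9. The SAP estimate therefore shifts by 0.257 × 0.303 = 0.078 SD or 0.257 × 0.101 = 0.026 SD. Its own standard error is √(2/30) × √0.6 = 0.200 or √(2/30) × √0.2 = 0.115, so the shift is 0.39 or 0.22 of a standard error.

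**SAP 8.4 subgroup models.** This is a Week 76 approximation by simulation, with k 1.0 to 1.4, ρ 0.7 to 0.9 and MMSE correlations of magnitude 0.6. In a sex-type subgroup, dropping the own baseline alone costs 0 to 11% of variance, and dropping both covariates costs 5 to 19%. In an MMSE split, dropping the own baseline costs 0 to 15%.

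**The case against.** The textual mismatch is not in dispute. The case against is about size and scope.

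- **Comparator.** The departure is from a protocol model that has the own baseline without MMSE. On that comparison the median variance ratio is only 1.015, and the SAP model is often the better one. This stands as a measure of the cost of departing from the protocol. The 1.00 to 1.56 range measures something else: what is lost by not simply adding the own baseline to the SAP model.
- **The 74% figure is one corner.** It needs k = 1, ρ = 0.6, a = 0.4 and b = 0.6. It should be read as an upper limit on the loss. In 54% of cells the ratio is below 1.10.
- **No bias.** Under randomisation, omitting a baseline covariate neither biases the contrast nor inflates type I error. This is correct, and neither is claimed here.
- **Section 10 is not used as a change log.** The new primary population is described elsewhere in the SAP and is not listed there either. True, but that population change is at least stated and explained; the covariate change is not.
- **The wording may not be exhaustive.** A model said to include three terms could contain more. However, the neighbouring model descriptions list their terms in full, and the covariate rule in 6.1.2 is limited to primary analyses.
- **SAP 8.4 contradicts nothing in the protocol.** Protocol 11.3 has no subgroup models. That part is a minor recommendation, and the main point does not depend on it.

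**Conclusion.** The concern holds. Protocol 11.3.3 and SAP 8.2 and 8.3 conflict on the covariate for CDR-SB, CSF and PET, and the change is not declared. Every other multiplicity-controlled endpoint keeps its own baseline, and CDR-SB controls access to three further endpoints.

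The size depends on correlations that the documents do not give. The precision loss runs from nothing to an appreciable loss of power, and is modest at the median of the assumed range. The actual power for CDR-SB is unknown: early termination and the restriction to the mITT set reduce the numbers, and 90% was never calculated for this endpoint. The reasons to act are that one confirmatory test should have one model, and that in these calculations adding the own baseline never increases residual variance. This should be corrected; it does not threaten the co-primary analyses. The CSF and PET part matters less because those endpoints are exploratory, and the subgroup part is minor because it lies outside the gate.

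**What to change.** Before unblinding:

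- **SAP 8.2:** fit CDR-SB change with treatment group, pooled site, baseline CDR-SB and baseline MMSE.
- **SAP 8.3:** add the endpoint's own baseline to the ANCOVAs for CSF and for imaging measured only at baseline and Week 76. Repeated plasma and MRI measures already have it through the MMRM.
- **SAP section 10:** record the departure from protocol 11.3.3, including the added pooled site and MMSE terms.
- **SAP 8.4 (optional, lower priority):** keep the own baseline, MMSE and their visit interactions for age, sex, ethnicity, race, ApoE4 and medication use. In the MMSE splits keep the own baseline by visit, with continuous MMSE optional. Where the endpoint's own baseline defines the subgroup, as with iADRS tertiles when iADRS is the endpoint, it may be left out.

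The cost is SAP wording plus one already collected covariate, and one degree of freedom, per ANCOVA. The change is cheap only while the study is blinded; SAP 2.6 keeps the blind until data lock.
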